## Abbreviations

AE	Adverse Event
CONSORT	Consolidated Standards of Reporting Trials
ED	Emergency Department
GCP	Good Clinical Practice
HCPC	Health and Care Professions Council
LPD	Lateral Patellar Dislocation
MRC	Medical Research Council
MRI	Magnetic Resonance Imagery
NHS	National Health Service
NIHR	National Institute for Health Research
NPC	New Patient Clinic
PROM	Patient Reported Outcome Measure
RCT	Randomised Controlled Trial
REC	Research Ethics Committee
SAE	Serious Adverse Event
SAMPL	Statistical Analyses and Methods in Published Literature
SOP	Standard Operating Procedure
TBC	To be confirmed
TIDieR	Template for Intervention Description and Replication

## SECTION 1. ADMINISTRATIVE INFORMATION

### SECTION 1.1 Title

Individualised exercise for adults with an acute lateral patellar dislocation: a feasibility study

### SECTION 1.2. World Health Organisation Registration Data Set

Data category	Information
Primary registry and trial identifying number	Clinicaltrials.gov Trial registration number: To be confirmed (TBC)
Date of registration in primary registry	TBC
Source(s) of monetary or material support	MRes Clinical Research National Institute of Health Research (NIHR) Studentship Award
Primary sponsor	City, University of London
Sponsor's reference	MRes/18-19/04
Contact for public queries	[name] [name] [contact] Email: [contact]
Contact for scientific queries	[name] [name] [contact] Email : [contact]
Public title	INDEX-KD: INDividualised EXercise for Kneecap Dislocations
Scientific title	Individualised exercise for adults with an acute lateral patellar dislocation: a feasibility study
Countries of recruitment	England
Health condition(s) or problem(s) studied	Primary and recurrent lateral patellar dislocation
Intervention:	Participants will be provided with up to 6 sessions of individualised physiotherapy over a maximum duration

	
of 3 months. Initially participants will be required to select their activity related goals from treatment. They will then commence a progressive exercise programme focussed on resolving acute knee impairments (i.e. swelling and reduced range of movement), improving lower limb strength and motor control, and facilitating a return to their activity related goals. The exercises chosen will be based on the physiotherapist's assessment, adapted to the participant's physical ability and agreed with the participant. Participants will be required to complete the exercises independently at least 3 times a week. Strategies to increase adherence will also be employed.

Key eligibility criteria	
Ages eligible for study: <math>\geq 16</math> years of age
 
Sexes eligible for study: both

	
Attending the John Radcliffe hospital trauma and orthopaedic service New Patient Clinic (NPC) or trauma outpatient physiotherapy department with an acute first time or recurrent traumatic or atraumatic lateral patellar dislocation (LPD)

Study type	Type of study: Interventional
	Study design: Prospective observational cohort
	Phase: Feasibility
Date of first enrolment	January 2019
Planned trial period	9 months
Target sample size	15
Recruitment status	Pending
Primary outcome(s)	
 
Eligibility (proportion of participants with a diagnosis of LPD screened for eligibility who satisfy the eligibility criteria)
 

	
 
• Recruitment rate (proportion of eligible participants who consent to participate in the study)
 
• Acceptability of the intervention (assessed by an internally designed participant satisfaction questionnaire and the proportion of participants lost to follow-up)
 
• Adherence (proportion of scheduled physiotherapy sessions attended, and prescribed exercise sessions completed)
 

Key secondary outcomes	
 
• Acceptability of outcome data collection (completion rates) of the following patient reported outcome measures (PROMs) at 3 months: 
 
➤ Tegner Activity Score
 
➤ Lysholm Knee Scoring Scale
 
➤ EQ-5D-5L
 
 
 
• Assess harms associated with participation in the study
 
• Determine what assessment findings are consistent with a diagnosis of LPD
 
• Assess delivery of the intervention
 

### SECTION 1.3. Protocol version

Date:	10/12/2018
Version:	2.0
Authors	[name] ( CF ), [name] ( MH ), [name] ( SH ), [name] ( DK )
Revision chronology	Nil

## SECTION 1.4. Funding

*CF* is funded by a NIHR Masters in Clinical Research studentship award. This protocol represents independent research funded by the NIHR. The views expressed are those of the authors and do not necessarily represent the views of the NIHR, National Health Service (NHS) or Department of Health.

*MH* is supported by the NIHR (NIHR Programme Grants for Applied Research RPPG-1210-12011). The views expressed in this publication are those of the author(s) and not necessarily those of the NHS, the NIHR or the Department of Health.

*SH* is a Senior Lecturer in Health Services Research and Health Psychology at City, University of London, who support his research. The views expressed in this publication are those of the author(s) and not necessarily those of City, University of London.

*DK* is supported by the NIHR (NIHR Post Doctoral Fellowship, [name], PDF-2016-09-056). The views expressed in this publication are those of the author(s) and not necessarily those of the NHS, the NIHR or the Department of Health.

### **1.5b Sponsor and funder**

The NIHR and City, University of London, had no role in study design and will have no role in implementation of the study, data collection and analysis, and decision to submit for publication.

## **SECTION 2. LAY SUMMARY**

### **Background**

Kneecap dislocations are relatively common, accounting for approximately 3% of all sports related knee injuries. It occurs most often in mid to late adolescence, during sports and activities that involve twisting and changing direction. Commonly encountered problems after this injury include reduced activity levels, an increased risk of osteoarthritis of the kneecap joint in later life, and feelings of kneecap instability during sport and dynamic activities such as hopping and changing direction. After this injury 20-50% of patients will suffer another dislocation.

There is a lack of evidence to support any one treatment for this condition but to help recovery most patients are referred for physiotherapy. The management of recurrent dislocation is more controversial as surgery is sometimes considered, but data we collected from our service shows that these patients are routinely referred for physiotherapy.

The best form of physiotherapy remains to be determined. In the NHS, the average duration of physiotherapy after a first-time dislocation is between 7 weeks and 3 months and

typically involves advice and exercises to restore movement of the knee, improve balance, and strengthen the muscles on the front of the thigh. The duration and content of physiotherapy for recurrent dislocation in the NHS is unknown. In the medical literature, published exercise programmes are poorly described, making it difficult to determine if they have been appropriately designed and of sufficient intensity. This variability in the duration and content of physiotherapy may explain the poor outcomes in this predominantly young, active population following this injury. Determining the optimal rehab programme therefore is a research priority

### **Aims of the research**

The aim of this study is to assess areas of uncertainty relating to the implementation of an individualised exercise programme for patients with a recent kneecap dislocation. This will help determine if a future larger study is feasible and inform the design and conduct of future research that would aim to optimise outcomes for people after a kneecap dislocation.

### **Research plan**

We aim to recruit 15 participants with a recent kneecap dislocation from the John Radcliffe Hospital. Participants will be enrolled in the exercise intervention which involves up to 6 physiotherapy sessions over a maximum of 3 months. Our exercise programme was designed using the best available evidence. The programme aims to increase leg muscle strength. There is also a focus on facilitating a return to the participant's usual activities, which may include dynamic activities such as hopping and changing of direction. The dynamic exercises differentiates it from other published exercise programmes. Participants will be required to perform the exercises at least 3 times a week independently. Strategies to increase adherence to the exercise programme will also be used.

The study objectives are to determine how many patients match our eligibility criteria, to determine the recruitment rate, and to assess the acceptability of the intervention to the participants. The feasibility of using eligibility criteria and collecting outcome measures that would be used in a future definitive study will also be assessed.

## SECTION 3 INTRODUCTION

### SECTION 3.1 Background and rationale

#### 3.1a Background

Lateral patella Dislocations are a relatively common injury of the knee, accounting for approximately 3% of sports related knee injuries. Incidence rates of primary LPDs range from 23.1 – 42 per 100,000 person years in the general population, are similar amongst males and females, and peak during mid to late adolescence.

50-60% of LPDs result from sporting activities, with the majority of these occurring during multi-directional and pivoting sports. The most common mechanism of injury is thought to involve a combination of knee flexion and femoral internal rotation on an externally rotated tibia, and has been compared to the non-contact anterior cruciate ligament mechanism of injury.

Recurrent LPD is a commonly encountered problem with 23-30% of patients suffering a recurrent LPD within 10 years. In younger patients this is significantly higher with recurrent ipsilateral LPD rates of 50% reported in patients under 18 years of age at 20 years follow-up. Additional negative sequelae include reduced activity levels, an increased risk of patellofemoral osteoarthritis, and persistent feelings of instability.

Due to a paucity of high-quality evidence the optimal management of LPD is unknown. There are currently no published clinical guidelines to guide the treatment of this condition in the United Kingdom (UK). Current expert opinion recommends conservative management in the form of physiotherapy for first time LPD, in the absence of an osteochondral lesion or fracture, with surgical intervention reserved for recurrent LPD. These recommendations however are made by clinicians based in the United States and do not necessarily reflect current practice within the NHS. We collected data on all patients with a diagnosis of LPD attending the John Radcliffe trauma service in 2017. This revealed that 76/94 patients with a diagnosis of LPD were referred for physiotherapy. Of these, 32 were first-time LPDs, 41 were recurrent LPDs and 21 were unknown. This indicates that both first-time and recurrent LPDs are routinely referred for physiotherapy in an NHS setting.

In the NHS, after a first-time dislocation, physiotherapy lasts on average between 7 weeks and 3 months and is comprised of advice, range of movement, proprioception and

strengthening exercises, but sport specific rehabilitation is rare. The duration and content of physiotherapy in the NHS for recurrent dislocations is unknown. Reviews of conservative interventions for LPDs has been unable to determine the most effective form of treatment, citing a lack of adequately reported interventions and well-designed trials comparing exercise interventions.

This absence of evidence to inform the design and conduct of rehabilitation programmes for this patient cohort may explain the poor outcomes in this predominantly young, athletic patient population. Determining the optimum rehab programme therefore remains a research priority

### **3.1b Rationale for this study**

Prior to conducting a future definitive trial, current Medical Research Council (MRC) guidelines for the development of complex interventions recommend conducting preliminary research to address areas of uncertainty, thereby informing the design and conduct of future research.

Our attempts to estimate the number of patients with an acute LPD matching our eligibility criteria attending the John Radcliffe trauma services has been limited by insufficient information available in the patient's medical records. This study aims to address this by determining how many patients with a LPD diagnosis satisfy our eligibility criteria.

Determining the recruitment rates will help estimate the duration of recruitment required for future studies. This is important given the difficulty in recruitment of participants to previous trials of conservative interventions for this condition in the UK.

As outlined previously, there is a paucity of evidence to inform the content of rehabilitation programmes after a LPD. There has been only one published Randomised controlled trial (RCT) comparing different exercise interventions which showed no clinically significant difference between general quadriceps strengthening exercise compared to vastus medialis specific strengthening exercise in a cohort of first-time LPD patients. Of note, there was an attrition rate of 52%, significantly limiting the utility of the results. The reasons for this are unknown but suggest aspects of the study design were not acceptable to the participants. Therefore, determining the acceptability of our intervention and data collection methods before a future definitive trial is important.

The poor reporting of interventions has been highlighted in a review of non-operative treatment for LPD. This makes it difficult to ascertain if the exercise interventions complied with current guidelines to optimise muscle strength. There was also wide variability in the exercises used. Only one study incorporated a running exercise into their programme and none reported using hopping, change of direction or sports specific exercises, or were inadequately described to determine if they did. This is particularly concerning as these are activities this patient cohort perceive to make their patella unstable and the majority of LPDs occur during sporting activities.

Although more progressive exercise programmes have been recommended, trials incorporating these programmes are absent.

### **SECTION 3.2 Objectives**

The aim of this study is to address uncertainty relating to key parameters and methodological processes in implementing an individualised exercise programme for patients with an acute LPD. It will identify aspects of the research design that are suboptimal and if these can be refined. This will provide preliminary evidence on the feasibility of future research, and if feasible, inform the conduct of this research.

Numerical targets for the primary objectives (e.g. 25% recruitment rate) to determine the feasibility of a future study have not been set. This is due to the small sample size and the difficulty in determining whether a larger scale study is feasible based on preliminary work, particularly as it is unknown a priori if the problems encountered can be resolved.

#### **3.2a Primary objectives**

- To determine the number of patients presenting with a diagnosis of LPD, screened for eligibility, who satisfy the eligibility criteria
- To determine the recruitment rates of eligible participants
- To determine the acceptability of the intervention to participants by using an internally designed patient satisfaction questionnaire and measuring the participant attrition rate (% of patients who fail to complete follow up data collection at 3 months)

- To determine participant adherence by measuring the proportion of scheduled physiotherapy sessions attended and prescribed exercise sessions completed by participant self-reporting

### **3.2b Secondary objectives**

- To determine the acceptability of outcome data collection to participants by measuring the completion rates of PROMs
- Assess harms associated with participation in the study
- To determine what assessment findings are consistent with a diagnosis of LPD.
- Assess delivery of the intervention

### **SECTION 3.3 Study design**

This study is a feasibility study as defined by the NIHR – a study conducted to provide further information about certain parameters to inform a future larger study, as opposed to a pilot study in which all aspects of a full study are conducted in a miniature form.

## **SECTION 4 METHODS: PARTICIPANTS, INTERVENTIONS AND OUTCOMES**

### **SECTION 4.1 Study setting**

Participants will be recruited from the John Radcliffe hospital only. Potential participants will be identified at the trauma service NPC or from referrals to the trauma outpatient physiotherapy department. Eligibility of potential participants identified at the NPC will be determined by a physiotherapist or orthopaedic surgeon working as part of the orthopaedic and trauma team. Eligibility of potential participants identified from referrals to the trauma outpatient physiotherapy department will be determined by *CF*.

### **SECTION 4.2 Eligibility criteria**

To reflect current local practice where patients with a diagnosis of LPD are routinely referred to a conservative management pathway with physiotherapy, all participants  $\geq 16$  years of age diagnosed with LPD by a member of the trauma and orthopaedic team will be considered eligible for the study.

#### **4.2a Inclusion and exclusion criteria**

Inclusion criteria:

- Male or female  $\geq 16$  years of age
- Attending the John Radcliffe trauma and orthopaedic service NPC or referred to the trauma outpatient physiotherapy department
- First time or recurrent LPD (traumatic or atraumatic) meeting the diagnostic criteria of 1) requiring reduction by paramedics **or** 2) diagnosed by a member of the trauma and orthopaedic team.

Exclusion criteria:

- Concurrent anterior cruciate ligament or posterior cruciate ligament injury confirmed by negative Lachman's and posterior drawer test or confirmed by Magnetic Resonance Imagery (MRI); medial collateral and lateral collateral ligament injury requiring application of a hinged knee brace or surgical repair; concomitant injury that would prohibit participation in the exercise intervention
- > 4 weeks from injury to presentation to acute care (ED or trauma services)
- Unable to give written informed consent
- Previous surgery on the affected knee
- Presence of fracture on plain radiograph including osteochondral fractures
- Medial patellar dislocation
- Considered inappropriate for referral to physiotherapy (by member of trauma and orthopaedic team assessing the patient)
- History of severe neuromuscular or congenital disorders
- Patients referred for orthopaedic opinion who are subsequently listed for surgery prior to completion of the study intervention
- Unable to understand written or spoken English
- Unable to attend physiotherapy sessions at the John Radcliffe trauma outpatient physiotherapy department

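### The cruciate-ligament exclusion contradicts itself: it treats negative examination tests as confirming an injury, and needs a one-line correction before screening starts

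*Combined protocol and SAP*

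**What the plan says.** Section 4.2a opens its exclusion list with concurrent cruciate injury, anterior or "posterior cruciate ligament injury confirmed by negative Lachman's and posterior drawer test or confirmed by Magnetic Resonance Imagery (MRI"). The same bullet goes on to collateral ligament injuries and to any "concomitant injury that would prohibit participation in the exercise intervention". A later bullet excludes patients whom the assessing trauma and orthopaedic team member considers unsuitable for physiotherapy referral.

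More than one person applies the list. Section 4.1 says: "Eligibility of potential participants identified at the NPC will be determined by a physiotherapist or orthopaedic surgeon" in the trauma team. For the other route it says: "Eligibility of potential participants identified from referrals to the trauma outpatient physiotherapy department will be determined by" the lead researcher, whom section 1.3 lists among the protocol's authors. Section 4.7a refers screeners to section 4.2a for the criteria.

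Section 4.4a makes two quantities that depend on the list primary outcomes: the percentage of screened patients with a lateral patellar dislocation (LPD) who are eligible, and the percentage of eligible patients who consent. Section 3.1b gives the count of eligible patients as a reason for the study: "This study aims to address this by determining how many patients with a LPD diagnosis satisfy our eligibility criteria".

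**The concern.** The criterion names an injury and then names, as its confirmation, a test result that does not confirm it. A screener who follows the words has two options. Either the examination part can never be met, so a cruciate injury is excluded under this clause only if MRI shows it, or exclusion attaches to patients whose tests are normal. The wording also leaves open whether the negative result governs both tests, and whether both are needed when the injury is to one ligament or the other.

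The criterion is an operative rule. If assessors resolve it differently, the eligibility percentage and the recruitment-rate denominator change with the reader and not with the patients. The lay summary adds a further reason to get the wording right: "The feasibility of using eligibility criteria and collecting outcome measures that would be used in a future definitive study will also be assessed". An exclusion that cannot be applied as written could be carried into later work.

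**Working it through.** This is mainly a check of text. Arithmetic serves only to show scale.

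**Text**

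1. Section 4.2a: the excluded condition is a cruciate injury, and the examination result said to confirm it is a negative test. The two conflict. The sentence is complete, so this is not a gap in the supplied text.
2. Elsewhere: neither test is named in any other section. The baseline assessment findings in section 5.1a (history, effusion or haemarthrosis, medial tenderness, apprehension) do not include them. Section 4.7a points back to section 4.2a. Nothing repairs the wording.
3. The MRI part is unaffected, but no section requires MRI for every patient, so the examination part has work to do.

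**Scale**

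Inputs:

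- Section 3.1a, on 2017 attendances: "This revealed that 76/94 patients with a diagnosis of LPD were referred for physiotherapy". The denominator is 94 LPD patients a year.
- Section 4.6a: 31 patients judged eligible and 51 of unknown eligibility, of whom 23 lacked only a recorded direction of dislocation.

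The protocol's own figure reproduces: 31 + 23 = 54 eligible a year, and 54/2 = 27 in 6 months.

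- Screened in 6 months, assuming the 2017 volume recurs: 94/2 = 47.
- Shift per patient classified differently: 1/47 = 2.1 percentage points.
- Illustrative eligibility: 27/47 = 57.4%.
- Standard error: sqrt(0.5745 × 0.4255 / 47) = 0.0721. Approximate 95% margin: 1.96 × 0.0721 = 0.141, or 14.1 points either way.

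The 57.4% is a low figure, because it counts the other 51 − 23 = 28 unknowns as ineligible. With every unknown counted as eligible, (31 + 51)/94 = 82/94 = 87.2%, and the margin at n = 47 is 1.96 × sqrt(0.8723 × 0.1277 / 47) = 0.095, or 9.5 points. At either end, one reclassified patient moves the estimate by much less than the sampling margin.

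The number of patients who would be classified differently cannot be derived, since no frequency of cruciate findings or test results is given.

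**The case against.** The strongest reply is that the practical effect is close to nil. The criterion is headed by an injury, so a patient with normal tests and no injury does not fall under it. The reading that excludes normal knees is strained, and it sits badly with section 4.2, which means to take in patients routinely sent for physiotherapy, and with the 31 patients in section 4.6a already judged eligible. Physiotherapists and surgeons will read the line by its purpose. Other provisions catch a missed injury: the MRI part, the concomitant-injury and referral exclusions, the eligibility review at the first appointment on the physiotherapy route (section 4.7a), and withdrawal of participants later found ineligible (section 5.1d). No feasibility threshold is at risk: "Numerical targets for the primary objectives (e.g. 25% recruitment rate) to determine the feasibility of a future study have not been set".

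Most of this stands, and it limits the severity. It does not make the sentence correct, and withdrawal after enrolment does not repair screening counts.

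Three narrower objections also have force.

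- The carry-forward argument is weak. Section 4.4b identifies the findings being tried for future eligibility criteria as those in section 5.1, and neither cruciate test is among them.
- The scale figures rest on a loose base. The documents do not say that the 31 and 51 are subsets of the 94, and section 4.7a adds referrals direct from the emergency department, so 47 may not be the number screened.
- One test per ligament is a natural reading, so how the tests combine is a secondary matter.

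**Conclusion.** The criterion is wrong as written, and the point is minor. Confidence is high for the wording; no effect on a primary outcome is demonstrated. The effect is zero if every screener reads the line by its purpose, and otherwise cannot be computed from the documents.

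The figure of 2.1 points per patient assumes that the 2017 volume recurs and that all 47 patients are screened. Section 4.6a lets recruitment stop early once 15 participants are enrolled. Fewer would then be screened, and each would weigh more. The 57.4% and 87.2% figures also assume that the counts in sections 3.1a and 4.6a describe the same patients, and they are for scale only.

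**What to change.** Before screening starts, the sponsor should reconcile the test result named in section 4.2a with the injury the criterion is meant to exclude. The same edit should state whether the two tests apply one to each ligament or together. What finding establishes the injury is for the clinical team to decide.

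The screening form should carry the identical wording and record which criterion an ineligible patient failed. Section 4.7a provides for recording reasons for declining, but the protocol does not mention recording reasons for ineligibility. The form is not among the documents and may already do this.

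The cost is one line in the protocol and matching wording on the form, with no extra patients or procedures. Section 1.2 gives recruitment as pending and first enrolment as January 2019, so on the protocol's own timetable the change can precede the first patient.
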